# **Secondary Safety Objectives**

Secondary safety objectives include:

- Assessment of change from baseline in visual acuity, intra-ocular pressure, retina or/and optic nerve abnormalities, and lens abnormalities at months 6, 12, 18, and 24.
- Evaluation of safety and tolerability of deferasirox FCT and phlebotomy over 24 months
- Evaluation of safety and tolerability of deferasirox FCT in subjects who interrupt due to  $SF \le 100 \ \mu g/L$  and re-initiate therapy when  $\ge 300 \ \mu g/L$ .

Unless otherwise specified, the following analyses will be performed by treatment arm on the Safety Set. All data, regardless of observation period, will be listed by treatment arm. Safety assessments starting during the pre-treatment or post-treatment period will be flagged in the listings. Safety assessments starting prior to study day 1 will appear with negative study day in the listings.

# 2.6.2 **Ocular Examinations**

Each ocular examination will be analyzed by eye side and treatment arm separately for the overall (on-treatment and post-treatment) period. The frequency and percentage of subjects with completed ocular assessments will be presented by eye side, evaluation type, timepoint, and treatment arm. Additionally, a summary for the number of ocular examinations performed at each time point will be presented by treatment arm. Furthermore, swimmer plots for key ocular assessments of interest will be generated along with dosing information to delineate the ocular assessments which were on the on-treatment and post-treatment periods. See additional details in (Ocular Assessments Section 5.3.2)

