2.1 Study rationale and purpose

Iron overload due to HH typically manifests between the third and sixth decades of life and is more common in males. If untreated, iron accumulates in the organs and causes tissue injury and dysfunction. Therefore, these patients might benefit from an iron chelator. If untreated in the liver, iron deposition will cause fibrosis, which may ultimately progress to cirrhosis and increased susceptibility to hepatocellular carcinoma. (Bacon 2011, Beaton and Adams 2007). Effects on the liver are exacerbated in alcoholics and in patients with chronic hepatitis B or C. Other manifestations include arthropathy, endocrinopathies (hypogonadism, sexual dysfunction, pancreatitis, or diabetes), and rarely, cardiomyopathy/cardiac failure with mortality (Niederau 1996, Morrison 2003).

Although phlebotomy is generally tolerated well and is very effective, it may not always be feasible due to inconvenient clinic visits and discomfort associated with the procedure; therefore, compliance may wane with time. A small percentage of patients may be ineligible for phlebotomy due to reduced venous access, congestive heart failure, or anemia. Oral iron chelation therapy will provide another option for patients either unwilling or unable to undergo a regular phlebotomy regimen.

The aim of this study is to evaluate the efficacy and safety of deferasirox FCT versus phlebotomy for the management of iron overload in adults with HH at risk of iron-related morbidity. This evaluation will provide information on the two treatment options in terms of the response rate of proportion of patients reaching the study target SF $\leq 100 \ \mu g/L$ and their associated safety profiles.

Ocular disturbances have been reported with deferasirox. Although no additional ocular risk have emerged over 10 years of Exjade on the market and from clinical trials, the FDA requires further confirmation on ocular safety with a controlled study in chelation-naive patients. Therefore, in addition to exploring the safety and efficacy of deferasirox FCT in HH, this study is being conducted to fulfill an FDA post-marketing requirement [PMC 750-10 (Exjade) /PMR 2888-8 (Jadenu)] to provide additional randomized data to confirm the ocular safety profile of deferasirox through detailed ophthalmologic assessments in patients treated with deferasirox FCT for 2 years.

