Patients should not make up missed doses. A missed dose is when the full dose is not taken within 8 hours of the usual time of the daily dose. Omit that day's dose, and resume with the next scheduled dose.

Dose adjustments for safety are allowed at any time and must be in increments or decrements of 3.5 or 7 mg/kg/day. For this study, the maximum dose of deferasirox FCT is 14 mg/kg/day.

Patients randomized to phlebotomy will receive treatment at a frequency determined by the treating physician's judgment for optimal iron control. Phlebotomy must be interrupted when a patient achieves the target SF $\leq 100 \ \mu$ g/L. Treatment may be re-initiated when SF $> 100 \ \mu$ g/L.

Patients randomized to deferasirox FCT are not allowed to receive phlebotomy during the study treatment.

Patients randomized to the deferasirox FCT arm who discontinued from treatment may receive phlebotomy during Post-treatment Ocular Follow-up at a frequency determined by the physician.

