# Visual Acuity

The visual acuity will be measured using an Early Treatment Diabetic Retinopathy Study (ETDRS) chart. A letter score is calculated based on the number of letters that can be correctly identified from specified distances. The ETDRS score entered into the CRF pages accounts for the distance at which the measurement was made (Section 1.1 of Manual of Ophthalmic Procedures for CICL670F2203); there will be no further adjustment while calculating logMAR. For low luminance and standard acuity measures, visual acuity will be described on a logMAR scale for all measures. For including acuity obtained with the ETDRS letters, the values will be converted to a logMAR scale, using the following formula (Beck et al, 2003):

where ETDRS score is the visual acuity ETDRS score. Finger counting, hand motion, and light perception will be assigned logMAR values of 2.0, 2.3, and 2.6 respectively (with a 0.3 logMAR increment per step). No light perception will be assigned a logMAR value of 2.9 (based on Lange et al, 2009).

The following shift tables will be generated using the categories (<0.1,  $\ge 0.1$  to <0.2,  $\ge 0.2$  to <0.3,  $\ge 0.3$  to <0.6,  $\ge 0.6$ ) by treatment group -

- Comparing baseline and *increases* from baseline in logMAR score category at each visit by eye side (right & left )
- Comparing baseline and *decreases* from baseline in logMAR score category at each visit by eye side (right & left)

Change from baseline (logMAR) = Post Baseline Value (logMAR) – Baseline Value (LogMAR)

Swimmer plots will be generated to show the change in the categories of logMAR at baseline versus scheduled visits by treatment arm and eye side. The on- treatment period will also be displayed on the plot.

The number and percentage of subjects with the following change from baseline for logMAR categories ( $<0.1, \ge 0.1$  to  $<0.2, \ge 0.2$  to  $<0.3, \ge 0.3$  to  $<0.6, \ge 0.6$ ) will be summarized by treatment arm for the overall period -

• the best change (decrease) in logMAR score category from baseline by eye side (right, left, best)

Novartis	Confidential	Page 24 of 36
SAP Amendment 1		Study No. CICL670F2203

• the worst change (increase) in logMAR score category from baseline by eye side (right, left, worst)

The changes from baseline at each visit will be calculated for assessments done in the same correction method as at baseline.

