#### 5.3.2 Ocular Assessments

Ocular data will be collected at screening visit, at week 24, 52, 76, 104 (EOT) visits. If two or more assessments performed within a time window, then the assessment closest to the planned visit is used in analyses by time window. When two values are equidistant from the planned assessment, the later one is used in analyses. The windowing defined is applicable for both on-treatment & post-treatment time periods. For the summaries by time point, we will be presenting the time points as defined below (Table 5-3).

For worst post-baseline assessment, all on-treatment values and post treatment values are considered regardless of time windows.

Table 5-4 shows the defined time windows.

Time point (Weeks)	Study Day	Lower Limit (day)	Upper Limit (day)
Baseline (Screening)	1*	-30	1
Week 24	162	2	259
Week 52	358	260	441
Week 76	526	442	623
Week 104	722	624	819

Table 5-4 Time windows for Ocular data

**End of Treatment -** Data collected at the EOT visit if conducted within 30 days of EOT date on disposition (DS) page in CRF.

For the post-baseline assessments among discontinued subjects, if no data were collected at the EOT visit the last available post-baseline on-treatment data will be used for EOT.

**\*Study Day 1** = first day of study treatment

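### Ocular examination results at Weeks 52, 76 and 104, and worst change, have no version limited to exams before treatment discontinuation

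*SAP*

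**What the plan says.** - **Period analysed.** SAP 2.6.2: "Each ocular examination will be analyzed by eye side and treatment arm separately for the overall (on-treatment and post-treatment) period". The visual acuity best- and worst-change counts "will be summarized by treatment arm for the overall period".
- **Windows.** SAP 5.3.2: "The windowing defined is applicable for both on-treatment & post-treatment time periods". When a window holds several exams, the "assessment closest to the planned visit is used in analyses by time window", with no preference for an on-treatment exam.
- **Worst value.** SAP 5.3.2: "For worst post-baseline assessment, all on-treatment values and post treatment values are considered regardless of time windows".
- **General rule.** The on-treatment paragraph of SAP 2.1.1 limits safety tables and figures to on-treatment data, but refers to 5.3.2 for ocular assessments. It therefore does not override the pooling.
- **Treatment after stopping.** Protocol 6.1.1: patients in the deferasirox arm "who discontinued from treatment may receive phlebotomy during Post-treatment Ocular Follow-up". Under the Safety Set definition they stay in the deferasirox arm.
- **What separates the periods.** SAP 5.3.2 defines an EOT time point: "Data collected at the EOT visit if conducted within 30 days of EOT date on disposition (DS) page in CRF". For discontinued subjects without such data it falls back on the last on-treatment exam. SAP 2.6.2 plans swimmer plots showing the two periods. The secondary safety section flags post-treatment assessments in listings, and SAP 2.3.1 flags deferasirox patients phlebotomised in follow-up.
- **Ocular adverse events.** SAP 2.5.2 analyses these on treatment and then repeats the analysis for the overall period.

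**The concern.** Protocol 2.1 says the study is to confirm ocular safety "through detailed ophthalmologic assessments in patients treated with deferasirox FCT for 2 years". Change from baseline at months 6, 12, 18 and 24 is a named secondary endpoint. For three of those four visits, the deferasirox row can include eyes examined months after the drug was stopped, in patients by then managed with the comparator.

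Two different errors can follow. In the by-visit tables, an effect on acuity, pressure, retina or optic nerve that recovers after stopping is averaged with recovered eyes and looks smaller. In the worst-change tables, a worsening that begins well after the drug was stopped is counted against deferasirox. The reader of the report would have no companion table showing how far either has happened. The plan provides that pair of analyses for ocular adverse events but not for the examinations.

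**Working it through.** **1. The plan's retention figure.** Inputs from Protocol 10.8 and SAP 3: 100 deferasirox patients, 24% dropout at month 6, 12% at month 12, at least 60 followed for 24 months.
- Month 6: 100 × (1 − 0.24) = 76.
- Month 12: 76 × (1 − 0.12) = 66.9.
- Reaching 60 needs year-two dropout of at most 1 − 60/66.9 = 10.3%. If the two rates are instead added, 64 remain at month 12 and the limit is 1 − 60/64 = 6.3%.

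Both are compatible with the stated assumption that dropout decreases, so 60 is reproducible as a planning figure.

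**2. How the windows treat one patient.** Take a hypothetical patient with last dose on day 300 and exams on days 169, 305 (EOT), 365, 533 and 729. The SAP on-treatment period ends on day 330.

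| Row (window, target day) | Exam used | Status |
|---|---|---|
| Week 24 (2–259, 162) | 169 | on-treatment |
| Week 52 (260–441, 358) | 365 | 65 days after last dose |
| Week 76 (442–623, 526) | 533 | 233 days after last dose |
| Week 104 (624–819, 722) | 729 | 429 days after last dose |

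The day 305 exam lies in the Week 52 window but is 53 days from target; day 365 is 7 days from target and displaces it. Day 305 then appears by time point only in the EOT row. The worst value is taken over two on-treatment and three post-treatment exams.

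**3. Off-drug share at Week 104.** Follow-up is open only after at least 6 months of assessments (Protocol 4.1.1). Assume that followed means on drug, so 60 are on drug at Week 104. Those who left after month 6 number 76 − 60 = 16. With uptake u, the share is 16u / (60 + 16u):
- u = 0: 0%
- u = 0.5: 8/68 = 11.8%
- u = 1: 16/76 = 21.1%

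**4. Effect on a by-visit contrast.** If the effect is fully reversible and off-drug eyes look like control eyes, observed excess = true excess × (1 − share). For an assumed 6-point excess and a 21.1% share: 6 × 60/76 = 4.7 points. An irreversible effect is not reduced.

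**5. Effect on worst change.** The worst value over a larger set of exams cannot be better than the worst over the on-treatment subset. Adding off-drug exams can only leave it unchanged or make it worse.

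**6. Which cut-off suits both arms.** Protocol 2.5 describes maintenance phlebotomy every two to four months. With intervals of 60 to 120 days, and exams assumed to fall evenly after the last blood removal, a cut at last removal + 30 days would exclude (60 − 30)/60 = 50% to (120 − 30)/120 = 75% of such patients' late exams. A cut at EOT date + 30 days avoids this.

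**The case against.** The strongest defence is that pooling is deliberate and reasonable. The protocol set up post-treatment ocular follow-up so that patients complete the month 6 to 24 schedule. The endpoint is worded by treatment arm without an on-drug restriction, and late or persistent eye changes can only be seen by following patients after they stop. The SAP history says the ocular analyses were revised to address a health authority request whose content is not visible. Everything is descriptive, and the key secondary endpoint, ocular adverse events, already has an on-treatment analysis. This is a good reason to keep the overall tables. It is no reason to omit a companion set, which the plan itself provides for ocular adverse events.

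Several stronger readings are tempting and are not supported:
- **No on-drug result at any visit.** Follow-up entry requires 6 months of assessments, so Week 24 is essentially on-treatment, and so is the EOT time point.
- **Swimmer plots are the only separation.** Listings flag the periods too. However, neither plots nor listings give a rate or mean change.
- **A 25 to 40% off-drug share.** This needs all 40 losses to occur after month 6 (20/80 to 40/100), which ignores the cited 24% month-6 dropout.
- **Dilution of worst change.** Step 5 rules this out. The error there runs in the cautious direction for a safety study, though it is still misattribution.

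**Conclusion.** The gap is real but limited. For Weeks 52, 76 and 104 and for worst change, no summary is restricted to exams before treatment discontinuation. Other outputs separate the periods only in part.

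On the plan's own dropout figures, off-drug exams make up 0 to 21% of the Week 104 deferasirox row, and an assumed fully reversible 6-point excess would appear as no less than about 4.7 points. This rests on four assumptions:
- The 24% month-6 dropout applies here. The plan hopes for better compliance with this formulation; if fewer leave early but only 60 remain on drug at Week 104, the share could be higher.
- The 60 patients followed are on drug. If that number includes patients in post-treatment follow-up, the share is also higher.
- Follow-up uptake, which the documents do not give, lies anywhere from none to all.
- The effect reverses fully.

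One group lies outside the calculation. Deferasirox is interrupted when ferritin reaches the target, and a responder who never restarts passes into the SAP's post-treatment period 30 days after the last dose while still attending treatment-phase visits. Such patients would add to the off-drug share by an amount that the documents do not allow one to estimate.

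**What to change.** In SAP 2.6.2 and 5.3.2:

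1. Keep the overall-period tables as planned.
2. Repeat the by-visit tables for Weeks 52, 76 and 104, and the worst-change tables, using only exams up to the EOT date on the disposition page + 30 days. That window is already in 5.3.2. Apply it in both arms. Choose the exam closest to target after this restriction, so that an EOT exam such as day 305 in the example is not displaced by a later one. Do not use last blood removal + 30 days, which would drop late control exams.
3. In the overall tables, show per visit and arm how many exams came after discontinuation and, for deferasirox, how many came more than 30 days after the last non-zero dose. The second count makes responders who never restart visible, because the EOT-based cut keeps them.

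The cost is SAP wording and one repeat of existing table shells; no new data are needed. The downside is smaller numbers at late visits and a subset that depends on who stays on treatment. The repeat therefore supports the overall tables and does not replace them.

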# Visual Acuity

The visual acuity will be measured using an Early Treatment Diabetic Retinopathy Study (ETDRS) chart. A letter score is calculated based on the number of letters that can be correctly identified from specified distances. The ETDRS score entered into the CRF pages accounts for the distance at which the measurement was made (Section 1.1 of Manual of Ophthalmic Procedures for CICL670F2203); there will be no further adjustment while calculating logMAR. For low luminance and standard acuity measures, visual acuity will be described on a logMAR scale for all measures. For including acuity obtained with the ETDRS letters, the values will be converted to a logMAR scale, using the following formula (Beck et al, 2003):

where ETDRS score is the visual acuity ETDRS score. Finger counting, hand motion, and light perception will be assigned logMAR values of 2.0, 2.3, and 2.6 respectively (with a 0.3 logMAR increment per step). No light perception will be assigned a logMAR value of 2.9 (based on Lange et al, 2009).

The following shift tables will be generated using the categories (<0.1,  $\ge 0.1$  to <0.2,  $\ge 0.2$  to <0.3,  $\ge 0.3$  to <0.6,  $\ge 0.6$ ) by treatment group -

- Comparing baseline and *increases* from baseline in logMAR score category at each visit by eye side (right & left )
- Comparing baseline and *decreases* from baseline in logMAR score category at each visit by eye side (right & left)

Change from baseline (logMAR) = Post Baseline Value (logMAR) – Baseline Value (LogMAR)

Swimmer plots will be generated to show the change in the categories of logMAR at baseline versus scheduled visits by treatment arm and eye side. The on- treatment period will also be displayed on the plot.

The number and percentage of subjects with the following change from baseline for logMAR categories ( $<0.1, \ge 0.1$  to  $<0.2, \ge 0.2$  to  $<0.3, \ge 0.3$  to  $<0.6, \ge 0.6$ ) will be summarized by treatment arm for the overall period -

• the best change (decrease) in logMAR score category from baseline by eye side (right, left, best)

Novartis	Confidential	Page 24 of 36
SAP Amendment 1		Study No. CICL670F2203

• the worst change (increase) in logMAR score category from baseline by eye side (right, left, worst)

The changes from baseline at each visit will be calculated for assessments done in the same correction method as at baseline.

A listing with the ETDRS score, logMAR score abnormalities and change from baseline categories will be provided for all subjects.

#### Tonometry

Descriptive statistics for the intraocular pressure at baseline, at each post-baseline visit and changes from baseline at each post-baseline visit will be presented, by eye and treatment arm. Box plot for intraocular pressure by eye side and treatment arm will be generated for the overall period.

The number & percentage of subjects with post-baseline values listed below will be summarized by treatment arm

- *at least one post-baseline* value <=5 mmHg, >5 to <=21 mmHg, >21 to <=30 mmHg, and >30mmHg by eye side (right, left, worst)
- the Increase from baseline IOP >=5mmHg to <10 mmHg & >= 10mmHg by eye side (right, left, best)
- the Decrease from baseline IOP >=5mmHg to <10 mmHg & >= 10mmHg by eye side (right, left, worst)

A listing of subjects will also be provided for this assessment.

Intraocular pressure will also be summarized in shift table (baseline and post baseline value at each time point) for each eye side considering the following categories:  $\leq 5$ ,  $\geq 5$  to  $\leq 21$ ,  $\geq 21$  to  $\leq 30$  and  $\geq 30$  mmHg for each of the treatment arms.

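### The tonometry table shows pressure rises for the best eye and falls for the worst eye, the reverse of the visual-acuity pairing, and defines neither label for a change in pressure

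*SAP*

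**What the plan says.** SAP 2.6.2 Ocular Examinations, Tonometry, plans counts and percentages of patients by arm in three rows. (The closing bracket falls just outside each quote.)

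- At least one post-baseline value in a fixed band: "value <=5 mmHg, >5 to <=21 mmHg, >21 to <=30 mmHg, and >30mmHg by eye side (right, left, worst".
- Rise: "the Increase from baseline IOP >=5mmHg to <10 mmHg & >= 10mmHg by eye side (right, left, best".
- Fall: "the Decrease from baseline IOP >=5mmHg to <10 mmHg & >= 10mmHg by eye side (right, left, worst".

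The same paragraph plans by-eye descriptive statistics of IOP and its change at each visit, and box plots. It adds: "Intraocular pressure will also be summarized in shift table (baseline and post baseline value at each time point) for each eye side". It also says: "A listing of subjects will also be provided for this assessment".

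Under Visual Acuity in the same SAP section, the corresponding rows are "the best change (decrease) in logMAR score category from baseline by eye side (right, left, best" and "the worst change (increase) in logMAR score category from baseline by eye side (right, left, worst".

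SAP 5.3.2 has the only general rule on worst values for ocular data: "For worst post-baseline assessment, all on-treatment values and post treatment values are considered regardless of time windows". It settles which time points are eligible, not which eye.

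**The concern.** On the logMAR scale the SAP ties the favourable direction to *best* and the unfavourable one to *worst*. For IOP it does the opposite. Opposite scales would explain that, but the scales are not opposite: Protocol 2.6 names IOP elevation among the ocular disturbances reported with deferasirox, so an increase is the direction of concern on both.

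The third column of each row is the one that combines the two eyes into one result per patient. The rise row is the only planned per-patient, across-eye count of numeric IOP increase from baseline. The study serves a post-marketing requirement on ocular safety, and change in IOP is a named secondary objective. A column that reports rises in the less affected eye would understate how many patients had one.

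**Working it through.** Neither document states a figure for this table, so there is nothing to reproduce. The check compares the texts and then shows what the choice of eye can do to the count.

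**1. Pairing.**

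| Measure | Increase shown for | Decrease shown for |
|---|---|---|
| logMAR (SAP 2.6.2, Visual Acuity) | right, left, worst | right, left, best |
| IOP (SAP 2.6.2, Tonometry) | right, left, best | right, left, worst |

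**2. Definition.** Neither the SAP nor the protocol says which eye is *best* or *worst* for an IOP change. Three readings are possible: the less affected eye, the eye with the largest change in the row's direction, or the better eye at baseline.

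**3. What the rise row would count for one patient.**

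| Change in the two eyes (mmHg) | Less affected eye | Eye with the largest change | Better eye at baseline |
|---|---|---|---|
| +12 and 0 | not counted | >=10 | >=10 or not counted |
| +12 and +6 | >=5 to <10 | >=10 | >=10, or >=5 to <10 |
| +12 and +12 | >=10 | >=10 | >=10 |

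**4. Bounds.** Let R and L patients out of N have a rise above the cut in the right and left eye.

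- A rise in either eye: from max(R, L) to min(R + L, N) patients. This is the count if the more affected eye is used.
- A rise in both eyes: from max(0, R + L - N) to min(R, L) patients. This is the count if the less affected eye is used.

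The planned arm sizes are 100 and 50 (SAP 3). The R and L values below are assumed.

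| N | R = L | Either eye | Both eyes |
|---|---|---|---|
| 100 | 2 | 2 to 4 (2-4%) | 0 to 2 (0-2%) |
| 100 | 5 | 5 to 10 (5-10%) | 0 to 5 (0-5%) |
| 50 | 2 | 2 to 4 (4-8%) | 0 to 2 (0-4%) |

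The two single-eye columns therefore do not fix the either-eye count.

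**5. Illustration.** Neither document gives a per-eye rate p or a between-eye correlation r, so both are assumed. P(both) = p² + r·p(1 - p), and P(either) = 2p - P(both). With p = 0.05 and r = 0.6, P(both) = 0.0025 + 0.0285 = 0.031 and P(either) = 0.10 - 0.031 = 0.069.

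| p | r | Both, per 100 | Either, per 100 |
|---|---|---|---|
| 0.02 | 0.3 | 0.6 | 3.4 |
| 0.02 | 0.9 | 1.8 | 2.2 |
| 0.05 | 0.6 | 3.1 | 6.9 |
| 0.10 | 0.3 | 3.7 | 16.3 |
| 0.10 | 0.9 | 9.1 | 10.9 |

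For p from 0.02 to 0.10 and r from 0.3 to 0.9, the either-eye count is about 1.2 to 5.4 times the both-eyes count.

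**6. Do the absolute bands stand in for the rise row?** Not fully. A rise of 10 from a baseline of 11 ends at 21 mmHg, and a rise of 5 from 16 also ends at 21. Both stay within the >5 to <=21 band, in the worst-eye row and in the shift tables.

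**The case against.** The strongest reply is that the harmful reading is not the natural one. In the visual-acuity rows the third column seems to take the eye with the most extreme change in the row's direction. Carried over to tonometry, the rise row takes the eye with the larger rise, no patient is lost, and only a word is wrong. This stands as a possibility, so an undercount is conditional. It does not dispose of the point: the label would still say *best* for the direction of concern, and two programmers could derive different columns from the same text.

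Second, the visual-acuity text gives a direction for best and worst change but no explicit rule for choosing the eye, so the missing definition is not peculiar to IOP. The absolute-value row also lists <=5 mmHg under *worst*, so the SAP follows low pressure as well as high. Pairing a fall with *worst* is therefore not plainly an error; the anomaly lies mainly in the rise row. Both remarks are fair.

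Third, other outputs show IOP rises. The right- and left-eye columns are themselves patient counts. Protocol 7.2.2.5 requires significant abnormal ocular findings that meet the adverse event definition to be recorded as adverse events, and SAP 2.6.3 counts these per patient whichever eye is involved. The listing would let a reader derive the either-eye count by hand. This limits the point to one column.

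**Conclusion.** The labels for IOP change are reversed relative to visual acuity and are undefined. That much rests on the text alone. The consequence depends on what *best* means. As the less affected eye, the across-eye column drops one-eyed rises and moves asymmetric bilateral rises to a lower band. As the eye with the largest change, the column is right and the label wrong. The counts in the working show what could happen under assumed inputs; they do not forecast this trial.

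A reader might infer that the plan hides IOP rises. The documents do not support that: the single-eye counts, by-eye change statistics, shift tables, worst-eye absolute bands, adverse event tables and listing do not depend on this label. A reader might also infer that the key secondary result is affected. It is not, because SAP 2.5.1 defines it by adverse events rather than by tonometry change. The primary endpoint is untouched, the analysis is descriptive, and no test depends on the row. This is a minor error.

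**What to change.** In SAP 2.6.2, Tonometry:

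- Change the rise row to *right, left, worst*. Define *worst* as the eye with the larger maximum post-baseline increase, using all on-treatment and post-treatment values, as SAP 5.3.2 does for worst assessments.
- Change the third column of the fall row to the eye with the larger decrease, and define it in the same way.

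The cost is a one-line definition and two changed labels, with no new data. If *best* had been programmed as the less affected eye, the derivation changes slightly and the across-eye count of rises may go up. If it had been programmed as the eye with the largest rise over the same values, no rise count changes.
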